3.0 Objectives

SPECIFIC AIMS

Degenerative disease of the lumbar spine (e.g., degenerative discs and facets, bulging discs) is ubiquitous in older adults, but low back pain is not.^{1,2} Treatment that focuses exclusively on degenerative spine disease such as spinal injection and surgery, therefore, has resulted in rising costs and exposure to potentially life-threatening morbidity but not improved outcomes.³ We posit that to improve treatment outcomes for older adults with chronic low back pain (CLBP – back pain that has been present on at least half the days for at least 6 months⁴), the condition should be approached as a syndrome, that is, a final common pathway for the expression of many contributors. Geriatricians evaluate and treat other syndromes, such as delirium and falls similarly, with good outcomes.⁵ When an older patient experiences delirium, a geriatrician doesn't recommend brain surgery. Using this model, the lumbar spine is considered a weak link, but is rarely the sole treatment target. Conditions that commonly contribute to pain and disability in older adults with CLBP such as hip osteoarthritis (OA), fibromyalgia, and depression, are associated with specific evidence-based treatments.

PURPOSE AND HYPOTHESES

The central question that the proposed randomized trial is designed to answer is: **What is the efficacy of comprehensive patient-centered care of CLBP as a syndrome that is delivered in Aging Back Clinics (ABC), compared with usual care (UC)?** Through prior VA Rehabilitation Research & Development support, we have developed and published evidence and expert-opinion based guidelines for the evaluation and treatment of 12 key contributors to pain and disability in older adults with CLBP – hip OA, fibromyalgia, myofascial pain, lumbar spinal stenosis, sacroiliac joint syndrome (SIJS), leg length discrepancy, lateral hip/thigh pain, insomnia, depression, anxiety, maladaptive coping, and dementia.⁶⁻¹¹ Our prior work also supports the commonplace nature of multiple contributors to CLBP in older Veterans and the feasibility of delivering ABC care that follows our published guidelines. We now wish to compare this approach to that of UC in older Veterans. Proof of the hypotheses that we will test could significantly

impact patient care by reducing pain and disability and avoiding costly and potentially morbid treatments. The proposed trial is designed to address the following aims:

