Aim 1: Establish the efficacy of ABC care compared to usual care.

We hypothesize that those randomized to ABC care will have:

H1.1: Greater 6-month reductions in pain-related disability as measured by Oswestry Disability Index (ODI; primary outcome and endpoint);

H1.2: Greater 12-month reductions in ODI; and greater 6- and 12-month reductions in pain severity (by PROMIS 29), quality of life (by PROMIS Global Health [GH]); depressive and anxiety symptoms (by PROMIS 29); and greater improvement in falls efficacy (by Falls Efficacy Scale-International short form);

H1.3: Less healthcare utilization between 6 and 12 months with respect to emergency room visits, hospitalizations, opioids prescribed, and invasive procedures performed (secondary outcomes and endpoints).

Aim 2: Explore the heterogeneity of treatment efficacy of ABC care.

H2.1: Those with greater baseline CLBP-associated disability, anxiety/depression, mild cognitive impairment, and/or obesity will reap greater benefits from ABC compared to UC (exploratory subgroup discovery).

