We will fit a linear mixed model with baseline to follow-up change in ODI score as the dependent variable; intervention arm (ABC/UC), follow-up time point (6/12 months) and their interaction as fixed effect of main interest; baseline ODI as a fixed effect covariate; and a participant random effect to account for multiple repeated assessments of the same participant over time. The statistical significance at $\alpha=0.05$ of the ABC vs UC means contrast at the 6-month point will serve as the formal test of the primary hypothesis H1.1. Upon confirming the H1.1 primary hypothesis, we will compute the number-needed-to-treat (NNT) as the reciprocal of the between-intervention difference in percentages of those showing a meaningful ODI improvement above its MCID.

Aim 1 Secondary Analyses:

To characterize the intervention actually received under ABC care, we will describe the conditions identified, further evaluations/initiated treatments and their responses recorded in the form that tracks response to treatment and additional management plans (see Appendix 12). We will employ the same analytic strategy described above for ODI (under primary analysis) for our secondary continuous outcomes pain severity, quality of life and falls efficacy. The statistical significance of the ABC vs UC means contrast at the 6- and 12-month points will serve as the formal tests of the secondary hypotheses H1.2.

Measures of healthcare utilization between 6 and 12 months in H1.3 (prescriptions/refills of opioids and inappropriate medications for elderly, invasive procedures, emergency room/hospital visits) are mostly in the form of counts. As such, we will fit a series of generalized linear models with each count utilization outcome as the dependent variable, a negative binomial distribution to account for any over dispersion and a logarithmic link function for the count outcome, actual person-time of exposure with opportunity for reporting utilization outcome as an offset, and intervention arm (ABC/UC) as the independent factor of interest. Intervention arm incident rate ratios and their statistical significances will constitute tests of H1.3.

Aim 2 Analyses:

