We will perform a series of sensitivity analyses to ensure the robustness of our results against various assumptions. One such analysis will involve inclusions of baseline participant characteristics significantly different between groups as additional covariates in the linear mixed and generalized linear models above. Another will involve sensitivity of results to missing data handling techniques. In addition, if analyses of residuals from the models show violations of statistical assumptions, we will consider fitting models after Box-Cox transforming¹⁰¹ the continuous variables. Finally, a reasonable alternative to the proposed negative binomial models for count data representing healthcare utilization measures is the zero-inflated Poisson model.¹⁰² We will examine the sensitivity of our findings for utilization outcomes against this alternative modeling strategy.

Sample Size Justification and Statistical Power:

Planned sample size is 310 participants. Prior data and assumptions include a between-subject standard deviation of 18 points for pre- to post-intervention change in the primary outcome ODI¹⁰³; a conservative estimate of a minimally clinically important difference (MCID) of 7 points¹⁰⁴; a conservative dropout rate of 15% from other back pain trials¹⁰⁵; using published methods implemented in commercial software (PASS 2012®, Number Cruncher Statistical Systems, Kaysville, Utah), with 310 patients and 280 anticipated completers, we will be able to detect an observed primary outcome difference as small as 7 points with 90% power in a 2-tailed test at the $\alpha=0.05$ level.

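### H1.2 and H1.3 are judged by 11 to 16 formal secondary tests with no gate on H1.1, no order, no multiplicity adjustment and no rule for success

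*Combined protocol and SAP*

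**What the plan says.** Section 5.6, Aim 1 Primary Analysis, defines the primary test clearly: "The statistical significance at $\alpha=0.05$ of the ABC vs UC means contrast at the 6-month point" decides H1.1.

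The next subsection, Aim 1 Secondary Analyses, applies the same mixed model to pain severity, quality of life and falls efficacy. It states that the ABC versus UC "means contrast at the 6- and 12-month points will serve as the formal tests of the secondary hypotheses H1.2". For utilization it fits one negative binomial model per count outcome and adds: "Intervention arm incident rate ratios and their statistical significances will constitute tests of H1.3".

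In section 3.0, H1.1, H1.2 and H1.3 all stand under Aim 1, the efficacy aim. H1.3 reads: "Less healthcare utilization between 6 and 12 months with respect to emergency room visits, hospitalizations, opioids prescribed, and invasive procedures performed (secondary outcomes and endpoints". H1.2 there also includes depressive and anxiety symptoms. Only the Aim 2 hypothesis is itself marked as exploratory.

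Neither section gives a significance level for the secondary tests, an order among them, a gate on H1.1, an adjustment, or the number of significant results needed for H1.2 or H1.3 to count as supported. The plan does use conditions elsewhere. The number needed to treat is computed only once H1.1 is confirmed, and subgroup effects are estimated only after a significant interaction.

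**The concern.** Section 5.6 gives the secondary results inferential status as tests of named efficacy hypotheses, but does not say what would count as passing. One significant contrast out of many could be reported as support for H1.2 or H1.3, even if the 6-month ODI test fails. The Purpose and Hypotheses text raises the stakes: "Proof of the hypotheses that we will test could significantly" affect patient care and help avoid costly or harmful treatment. The avoidance of such treatment is mainly the subject of H1.3.

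The outcome list is not settled either. Depression and anxiety appear in H1.2 in section 3.0 but are not named in the section 5.6 analysis. Inappropriate medications appear in section 5.6 but not in H1.3. An open list with no error control leaves room for selective emphasis.

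**Working it through.** **1. The plan's own figure.** No familywise error rate is stated for the secondary tests. The one design calculation concerns H1.1: "a between-subject standard deviation of 18 points for pre- to post-intervention change in the primary outcome ODI", "a conservative estimate of a minimally clinically important difference (MCID) of 7 points", and 280 completers (140 per arm at 1:1). The standardised effect is 7 / (18 × √(2/140)) = 3.254. Power ≈ Φ(3.254 − 1.960) = 0.902, or 0.900 with the noncentral t. This agrees with the stated "as small as 7 points with 90% power in a 2-tailed test". It covers H1.1 only.

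**2. Counting the tests.**

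| Source | H1.2 | H1.3 | Total |
|---|---|---|---|
| Section 5.6 list | 12-month ODI (1) + 3 outcomes × 2 times (6) = 7 | opioids, inappropriate medications, invasive procedures, emergency/hospital visits = 4 (5 if visits are split) | 11–12 |
| Section 3.0 list | 12-month ODI (1) + 5 outcomes × 2 times (10) = 11 | emergency visits, hospitalizations, opioids, invasive procedures = 4 | 15 |
| Both lists combined | 11 | 5 | 16 |

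**3. Chance of a false result if ABC has no effect on any outcome.** Assumptions:
- each test is two-sided at 0.05, so 0.025 in the direction favouring ABC;
- any one significant result is taken as support;
- the test statistics are normal with equal correlation ρ. The documents give no correlations, so ρ is varied from 0 to 0.8.

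For independent tests the chance is 1 − (1 − a)^k:
- favouring ABC: 1 − 0.975^11 = 0.243; 1 − 0.975^16 = 0.333;
- either direction: 1 − 0.95^11 = 0.431; 1 − 0.95^16 = 0.560.

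For ρ > 0, condition on the shared normal component u and integrate. In the favourable direction this is 1 − ∫ φ(u) Φ((1.96 − √ρ·u)/√(1 − ρ))^k du.

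| Tests | Direction | ρ = 0 | 0.3 | 0.5 | 0.8 |
|---|---|---|---|---|---|
| 11 | favouring ABC | 0.243 | 0.191 | 0.152 | 0.090 |
| 16 | favouring ABC | 0.333 | 0.244 | 0.188 | 0.104 |
| 11 | either | 0.431 | 0.375 | 0.304 | 0.180 |
| 16 | either | 0.560 | 0.476 | 0.374 | 0.207 |

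A more structured set of assumed correlations gives results inside these ranges. With the same outcome across times at 0.5–0.8, different outcomes at 0.3–0.7 and utilization at 0.1–0.4, the chance of a false result favouring ABC is 14–21% for 11 tests and 17–27% for 16.

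**4. Effect of the remedies.** If ABC does nothing at all, a gate on H1.1 holds the chance of any secondary claim to at most 5% (2.2–4.3% in simulation). The gate alone gives no protection within the secondary family when H1.1 is truly positive. Holm at 0.05 over the family does: its first threshold is 0.05/11 = 0.0045 or 0.05/16 = 0.0031.

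**5. Price of Holm.** An effect with 90% power at two-sided 0.05 has a standardised mean of 1.960 + 1.282 = 3.242. At the first Holm step of 10 tests (0.0050, critical value 2.807), power is Φ(3.242 − 2.807) = 0.67. At the first step of 15 tests (0.0033, critical value 2.935), it is Φ(3.242 − 2.935) = 0.62. These counts apply if one of 11 or 16 tests is placed ahead of the rest. With all 11 or all 16 in the Holm family the figures are 0.66 and 0.61.

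**The case against.** The case for leaving the plan alone has several parts.

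- **A false efficacy claim is not likely.** A reader might infer from the absence of control that a false secondary claim is more probable than not. The figures do not support that. A false result favouring ABC stays at or below about one in three. In the tables above, only 16 independent tests counted in both directions pass one half. This stands.
- **The plan does not say that one significant contrast suffices.** Section 3.0 joins the components of H1.2 and H1.3 with *and*. If every component had to succeed, no adjustment would be needed and the rates above would not apply. This stands in part: the any-one rule is an assumption, but the plan does not adopt the all-must-succeed rule either.
- **The 0.05 level is stated only for H1.1.** True. It is inferred for the secondary tests from the instruction to use the same analytic strategy.
- **A primary-over-secondary ranking exists.** H1.2 and H1.3 are labelled secondary, so it would be wrong to say that the plan has no hierarchy at all. What is missing is an order among the secondary tests and a gate on H1.1.
- **The section 5.6 overview mentions other exploratory analyses next to the secondary ones.** That phrase does not make H1.2 and H1.3 exploratory when the same section goes on to call their contrasts formal tests.
- **The text on proof of the hypotheses is motivation, not a decision rule.** Fair. It shows what is at stake, not how success is declared.

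Unadjusted secondary outcomes are acceptable when declared supportive. This plan does not declare them so.

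**Conclusion.** The point holds as a gap in error control and in the definition of success for H1.2 and H1.3. Section 5.6 treats 11 to 16 contrasts and rate ratios as formal tests under the efficacy aim. It gives no gate on H1.1, no order, no adjustment and no success rule.

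On the assumptions of two-sided 0.05 per test, any one significant result counting as support, no true effect, and equal correlation between 0.8 and 0, the chance of at least one false result favouring ABC is about 9–24% for 11 tests and 10–33% for 16. That is roughly 4 to 13 times the 2.5% for one test. Counting both directions it is about 18–43% and 21–56%.

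The H1.1 test and its power are unaffected. What is limited is how far the trial can claim 12-month, patient-reported or utilization benefits as established.

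**What to change.** In section 5.6, Aim 1 Secondary Analyses, replace the two statements that make these results formal tests with wording such as: *Results for H1.2 and H1.3 are supportive. They will be reported as estimates with 95% confidence intervals, unadjusted for multiplicity, and no claim of proven efficacy will rest on them.*

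Use a single outcome list in sections 3.0 and 5.6. Decide whether depression, anxiety and inappropriate medications belong in it, and whether emergency and hospital visits are one outcome or two.

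If the sponsor wants confirmatory secondary claims, test them only after H1.1 is significant and control the familywise error over that fixed list, for example with Holm at two-sided 0.05. The sponsor should choose any ordering in advance. The list must be settled first, because the Holm thresholds depend on its length.

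The cost of the supportive wording is a few sentences, with no new data, participants or procedures and no change to the primary test. Secondary results could then no longer be called confirmed on an unadjusted p-value. The confirmatory route costs more: an effect with 90% power at 0.05 falls to about 62–67% at the first Holm step of 15 or 10 tests.

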5.5 Study Evaluations

Screening Procedures (Appendix 7): Telephone screening by the RC (approved via a waiver of consent) using a structured questionnaire will determine participant eligibility, i.e., CLBP, ability to participate for up to 12 months, no red flags or prohibitive communication impairment, and no acute medical or psychiatric illness. If the screening procedures indicate that the Veteran is eligible, (s)he will be invited to come in for on-site baseline testing. After the participant has signed the HIPAA and Informed Consent documents they are considered enrolled. Then, the RC will administer the MMSE and those who fail (i.e., screen positive for dementia with a score $<$ 24) will be excluded and their PCP notified. We use the MMSE because it has been

studied extensively, has good diagnostic accuracy (sensitivity 0.85, specificity 0.9) and it takes only 5 to 7 min to administer.⁸⁵ Then a doctor who is part of this study will perform a Red Flags Screening. After this is complete, participants will be considered active participants in this study. Beyond the data measures that must be collected on site (MMSE, gait speed, and Red Flags Screening by provider), the remaining may be collected over the telephone or on site.

Baseline Testing (Appendix 8) - On all enrolled participants, RCs will collect a set of established measures that assess constructs relevant to older adults and have low participant burden, as shown in Table 6.

1. The **Oswestry Disability Index (ODI)**: Our main outcomes measure, the ODI assesses interference of pain with function.¹²
2. The **Minimal Data Set (MDS)**, recommended by the NIH Task Force on research standards for CLBP, measures pain severity and interference with daily activities, widespread pain, prior CLBP treatments, overall physical function, depressive symptoms, sleep, psychological maladaptation (i.e., fear-avoidance beliefs and catastrophizing), alcohol/drug use, cigarette smoking, demographics (age, race, ethnicity, gender, education, marital status), height and weight.⁴
3. The **PROMIS 29** collects items not already included in the MDS - anxiety symptoms, fatigue, and participation in social roles and activities.¹⁴ The full PROMIS 29 will be administered during follow-up.
4. **Other key cofactors** that may impact outcomes, and are relevant to older Veterans:
 - a. Medical comorbidity will be measured by self-report with the Duke comorbidity index.⁸⁶

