The goal is to explore whether ABC vs UC differences in improvement vary across participant subgroups of interest (effect modification). We will add each of the subgroups (based on baseline CLBP-associated disability, anxiety/ depression, mild cognitive impairment and obesity) and associated subgroup \times intervention group interaction effects as additional fixed effects in the above statistical models. Rigorous methodological guidelines for subgroup analyses require significant interaction effects for making conclusions of differential intervention effects in subgroups.⁹⁹ As such, we will first construct difference-in-difference type means contrasts representing the difference in ABC vs UC effects in different subgroups at each of the follow-up time points. If and only if the said interaction contrast is significant, we will estimate ABC vs UC differences and

their statistical significance within those subgroups.

Missing Data:

The best approach for handling missing data is to prevent it. We will use the methods described earlier to retain participants and prevent missing data. Despite our best efforts, missing data will occur. We will clearly document those with missing data and reasons in the CONSORT diagram, and compare those with missing data to complete data with respect to available data. Statistical guidelines for handling missing data recommend methods such as multiple imputation, which considers the uncertainty involved in imputing missing data.¹⁰⁰ Multiple imputation is arguably the best available objective method to analytically account for missing data under the ignorable or missing-at-random (MAR) assumption. Specifically, we will generate M=5 imputed values for each missing value, analyze the 5 datasets as though complete, and finally combine the results appropriately so that they reflect the uncertainty involved in imputation. SAS® MI and MIANALYZE procedures will be used. Other approaches to missing data, including the naïve approaches of ignoring the missing values and last-value-carried-forward (LVCF) will also be considered in sensitivity analyses and robustness of the results to using these approaches will be examined.

Sensitivity Analyses:

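### Aim 2 tests disability and symptom scores as subgroups with no stated cut-points; cutting a roughly normal score in two would lose at least 36% of the information on a linear interaction

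*Combined protocol and SAP*

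**What the plan says.** H2.1 in section 3.0 reads: "Those with greater baseline CLBP-associated disability, anxiety/depression, mild cognitive impairment, and/or obesity will reap greater benefits from ABC". The same line labels the aim "exploratory subgroup discovery".

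Section 5.6, Aim 2 Analyses, states the method: "We will add each of the subgroups (based on baseline CLBP-associated disability, anxiety/ depression, mild cognitive impairment and obesity", each with a subgroup-by-arm interaction added to the Aim 1 models. For the test, "we will first construct difference-in-difference type means contrasts representing the difference in ABC vs UC effects in different subgroups", at each follow-up time point (6 and 12 months in the ODI model). Effects within subgroups are estimated only if the interaction contrast is significant.

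The baseline measures behind the modifiers are described in section 5.5:

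- **Disability:** the main outcome measure, where "the ODI assesses interference of pain with function".
- **Anxiety and depression:** the PROMIS-29 "collects items not already included in the MDS - anxiety symptoms, fatigue", so depressive symptoms at baseline come from the NIH Minimal Data Set (MDS). Section 3.0 is less specific and lists depressive symptoms under the PROMIS-29.
- **MCI:** the QMCI, used as a screen.
- **Obesity:** height and weight, from the MDS.

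The ODI model already has "baseline ODI as a fixed effect covariate". No section gives a cut-point or a number of groups for any modifier. Neither Aim 2 nor the sensitivity analyses include a continuous modifier-by-arm term.

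**The concern.** H2.1 says that people with greater baseline disability gain more from ABC. The direct test of that statement is whether the ABC-UC difference changes with the ODI score. A contrast between subgroups treats everyone on one side of a cut as alike, so it uses less of what was measured.

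Two things are at stake. The first is power: interactions are harder to detect than main effects, and coarse grouping makes this worse. The second is predictability. The rule that opens within-subgroup estimates depends on a significant contrast, and that contrast depends on a grouping the plan leaves open.

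**Working it through.** **1. The plan's own power figure.** Inputs: SD of ODI change 18, difference 7, 280 completers, two-sided alpha 0.05 (section 5.6, Sample Size Justification); 1:1 allocation (section 5.5).

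- SE = 18 × √(2/140) = 2.151
- Power = Φ(7/2.151 − 1.960) = Φ(1.294) = 90.2% (90.0% with the noncentral t)

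The stated 90% is reproduced. The plan gives no power figure for Aim 2.

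**2. Information kept by a two-group split.** This is the squared correlation between the score and its split version. For a normal score with share p above cut c, it equals φ(c)² / [p(1−p)].

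| Split | φ(c) | Share kept | Lost |
|---|---|---|---|
| 50/50 | 0.3989 | 0.1592/0.25 = 0.637 | 36% |
| 30/70 | 0.3477 | 0.1209/0.21 = 0.576 | 42% |
| 20/80 | 0.2800 | 0.0784/0.16 = 0.490 | 51% |

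The median is the most favourable cut, so 36% is the minimum loss for two groups. It leaves an effective 0.637 × 280 ≈ 178 participants.

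**3. Power.** With a continuous term, the SE of the between-arm difference in slope, per moderator SD, is 2 × 18/√280 = 2.151. An interaction of (1.960 + 0.842) × 2.151 = 6.03 ODI points per SD therefore has 80% power. The same effect after a split:

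- Median: Φ(√0.637 × 2.802 − 1.960) ≈ 61%; simulation (3,000 runs, N = 280) gave 59%.
- 30/70: Φ(√0.576 × 2.802 − 1.960) ≈ 57%; simulation gave 55%.

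The split model in the simulation contained the split variable only, without the continuous score beside it.

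**4. More than two groups.** For k equal groups of a normal score, the share kept is the variance of the group means: 0.793, 0.861 and 0.897 for k = 3, 4 and 5. The losses are 21%, 14% and 10%. They apply to an ordered trend contrast (or top versus bottom for tertiles). A joint test on three or four groups has only about 60% or 57% power where the continuous test has 80%.

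**5. Other shapes.** At a median split, a uniform or clearly bimodal score loses about 25% and a right-skewed one 45% to 52%.

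**6. In ODI points.** Equal halves give a difference-in-difference SE of 18 × √(4/70) = 4.30, so 80% power needs 4.30 × 2.802 ≈ 12.1 points. The means of the two halves of a normal score lie 4 × 0.3989 = 1.596 SD apart. The continuous test therefore reaches 80% power when the halves differ by 6.03 × 1.596 ≈ 9.6 points. Splitting moves the requirement from about 9.6 to about 12.1.

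The stated 15% dropout would leave 310 × 0.85 = 263.5 completers, fewer than the stated 280. The shares lost in steps 2, 4 and 5 do not depend on which is used.

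**The case against.** The strongest reply is that the plan never says two groups, and that Aim 2 is exploratory with a significant interaction already required before any subgroup estimate. Both facts are correct. A reader might infer that the plan throws away a third or more of the information. The documents do not support that as a statement of fact: it needs a two-group cut, a roughly normal score and a linear effect. If the effect changes abruptly exactly at the cut, nothing is lost.

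Three other tempting readings also go too far.

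- **All four modifiers are graded.** H2.1 clearly grades disability, but it names MCI and obesity as conditions. MCI also works as a status in the trial: the PCP is alerted (section 5.4), and ABC providers may apply the Dementia algorithm to those with MCI (sections 5.1 and 5.5). A category is a legitimate question there.
- **Cut-points will be chosen after the data are seen.** The plan is silent, and silence is not a stated intention. For MCI some classification is needed at baseline to trigger the alert.
- **An ODI subgroup beside the continuous ODI covariate is an error.** That model can be fitted, and the duplication does not bias the interaction test. It is only coarser than necessary.

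It is also fair to say that most of the difficulty is common to any interaction test at this sample size. The move from 9.6 to 12.1 points is the part that grouping adds. What survives is that score-based modifiers are grouped by an unstated rule, with no continuous test planned.

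**Conclusion.** The point holds as a cheap improvement to an exploratory aim. For baseline ODI and the symptom scores, a continuous interaction is a more direct and more efficient test of H2.1 than subgroup contrasts with undefined groups.

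The size depends on what the undefined grouping turns out to be: at least 36% of the information for a two-group split, with power falling from 80% to about 60% at the median, and about 21% to 10% for three to five ordered groups tested for trend. These figures assume a roughly normal moderator and a linear interaction. The power figures also assume SD 18 and 280 completers. The main analyses use multiple imputation and adjust for baseline ODI, so the effective number and the point values are guides. The primary analysis is unaffected.

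**What to change.** Amend the Aim 2 text in section 5.6 as follows.

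- **Baseline ODI, anxiety and depressive symptoms:** make the Aim 2 test a continuous score-by-arm interaction, read at the follow-up time points already planned. In the ODI model this needs score-by-time and score-by-arm-by-time terms. Use the existing baseline ODI covariate for the ODI interaction.
- **Name the scores:** PROMIS-29 for anxiety and the MDS for depressive symptoms, as in section 5.5. The plan writes these two as a pair, so state that they are tested separately.
- **Check and display:** examine linearity with a spline, and show the ABC-UC difference at the 25th, 50th and 75th percentiles of each score.
- **MCI and obesity:** keep the categorical subgroup tests, at QMCI and BMI cut-points fixed before unblinding. Add continuous QMCI and BMI interactions as supporting analyses.

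No new data are needed. The cost is SAP wording and reliance on linearity, which the spline checks.
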